Patients with CI-DME who are willing to participate in the study and have given informed consent will undergo a thorough screening examination within 4 weeks of study treatment administration. The screening procedures, as outlined in the SoA, will include review of inclusion and exclusion criteria, medical history, physical examination, assessment of vital signs and ECG, serum pregnancy test for females of childbearing potential, and safety laboratory parameters. A predefined set of imaging criteria for eligibility will be confirmed by a Central Reading Center before enrolment.

Treatment Period

On Day 1, baseline assessments will be conducted on the eligible patients, according to the SoA. Patients will receive their first IVT injection of either RO6867461 or comparator therapy according to the randomization schedule and following established standard procedures. Patients will return to the eye clinic *every 4 weeks* for study *drug* administration and assessments as outlined in the SoA.

A post-treatment administration check of study eye will be performed for each patient immediately after study treatment administration by testing finger count vision, hand motion, and light perception, as appropriate. On the day of dosing, IOP will be monitored at 30 minutes post-administration in the study eye, using either Goldmann tonometry or Tono-pen, and if IOP \geq 30 mmHg in the study eye, IOP should be re-assessed at 1 hour post-treatment administration. If IOP continues to be elevated, treatment should be undertaken at the discretion of the investigator.

Observational Period

Patients will return for evaluation every 4th week. If during any of these evaluations the patients meet the pre-specified criteria, the patients will receive a single dose of 0.3 mg ranibizumab, exit the study, and receive a follow up phone call 7 days after the dose of ranibizumab to evaluate any potential adverse events. Otherwise, patients will exit the study once they have completed the observational visit at week 36.

STATISTICAL METHODS

PRIMARY ANALYSIS

The primary efficacy analyses will include all randomized patients, with patients grouped according to the treatment assigned at randomization.

The primary efficacy variable is the BCVA change from baseline to Week 24. The primary efficacy analysis will be performed using a Mixed Model for Repeated Measurement (MMRM) model.

[figure not shown]
RO6867461—F. Hoffmann-La Roche Ltd

Statistical Analysis Plan BP30099

21

PHARMACOKINETIC ANALYSES

A nonlinear mixed effects modeling approach (with NONMEM software) will be used to analyze the concentration-time data of RO6867461. Population and individual primary PK parameters (i.e., clearances and volumes) will be estimated, and the influence of various covariates (e.g., gender, body weight, etc.) on these parameters will be investigated. The data collected in this study may be pooled with data collected in the previous Phase I study, as appropriate, to build a PK model. Secondary PK parameters such as area under the concentration-time curve (AUC) and maximum plasma concentration observed (C_{max}) will be derived from the individual post-hoc predictions. The results of this analysis will be reported in a separate document from the Clinical Study Report.

SAMPLE SIZE JUSTIFICATION

The sample size is based on the primary efficacy outcome of mean change in BCVA from baseline *at Week 24 in the treatment-naïve patients*. Each RO6867461 dose (Arms B and C) will be compared with the control group (Arm A).

Consider 50 *treatment-naïve* patients randomized to Arm A, B, and C, with a drop-out rate of 10%. Assuming a standard deviation of 11 letters, this sample size provides approximately 80% power to detect a true difference of 5 letters at the one-sided α level of 10%. The minimum detectable difference is approximately 3 letters.

Approximately 60 previously IVT anti-VEGF treated patients will be enrolled in addition for exploratory analyses.

INTERIM ANALYSES

Two efficacy interim analyses to inform about possible future development options for RO6867461 are foreseen. They will not influence the study conduct. One interim efficacy analysis is foreseen after approximately 28 treatment-naïve patients in each arm have completed the Week 24 visit, and one when approximately all patients have completed the Week 24 visit.

A safety analysis will be performed if safety issues have been identified during ongoing review of the masked data.

Up to two additional interim analyses may be conducted for efficacy.

OTHER CONSIDERATIONS

NA

LIST OF PROHIBITED MEDICATIONS

Concomitant Therapy

Patients who use maintenance therapy other than those required to treat DME should continue its use.

PRP is permitted in either eye, if clinically indicated *for the treatment of proliferative diabetic retinopathy or retinal holes or tears post randomization.*

The decision to administer antimicrobial drops before and after the IVT administration is at the discretion of the investigator.

Prohibited Therapy

At the discretion of the investigator, patients may continue to receive all medications and standard treatments administered for other conditions, except the following:

- Concurrent use of systemic anti-VEGF agents
- Concurrent use of IVT anti-VEGF therapy in the fellow eye within 7 days preceding or following the study eye treatment
- Concurrent use of IVT or subtenon corticosteroids in study eye, except as required to treat adverse events

Appendix 2

Schedule of Assessments

Week	Screening D-28 to D-1	Week 1		Week 4	Week 8	Week 12	Week 16	Week 20	Week 24 ⁱ	Week 26 ^m	Week 28 ⁱ	Week 32 ⁱ	Week 36 ⁱ	Early Terminatio n Visit	Unschedul ed Visit
		Day 1	Day 7	Day 28	Day 56	Day 84	Day 112	Day 140	Day 168	Day 182	Day 196	Day 224	Day 252		
Day		0	144	648	1320	1992	2664	3336	4008	4344	4680	5352	6024		
Time Relative (h)				+/-3	+/-7	+/-7	+/-7	+/-7	+/-7	+/-7	+/-7	+/-7	+/-7	+7	
Visit Window															
Assessments															
Informed Consent	X														
Eligibility	X	X ^a													
Demography	X														
Medical History	X	X ^a													
Physical Examination	X								X					X	
Anthropomet ric Measuremen ts	X								X					X	
Vital Signs ^a	X	X ^b	X	X	X	X	X	X	X	X	X	X	X	X	X
ECG-12 lead ^a	X								X					X	X
Hematology ^a	X					X			X ^c					X	X
Blood Chemistry ^a	X					X			X ^c					X	X
Urinalysis ^a	X					X			X ^c					X	X
Coagulation ^a	X					X			X ^c					X	X
Hormone Panel ^b	X														
Pregnancy Test ^c	X														X
Administrati on of Study Drug ^{c,d}		X		X	X	X	X	X							X
Administrati on of 0.3 mg ranibizumab ^c									X ^c		X ^c	X ^c	X ^c		
Safety Finger Count Vision ^{c,d}		X		X	X	X	X	X	X ^c		X ^c	X ^c	X ^c		X

RO687461—F. Hoffmann-La Roche Ltd
Statistical Analysis Plan BP30099

IOP ^{a,j}	X	X ^k	X	X	X	X	X	X	X	X	X	X	X	X	X	X
BCVA ^{a,k}	X	X ^k	X	X	X	X	X	X	X	X	X	X	X	X	X	X
Slit Lamp ^a	X	X ^k	X	X	X	X	X	X	X	X	X	X	X	X	X	X
Indirect Ophthalmoscopy ^a	X	X ^k	X	X	X	X	X	X	X		X	X	X	X	X	X
Fundus Photography ^{a,c}	X	X ^{k,o}							X		X ^a	X ^a	X ^a	X	X	X
SD-OCT ^{a,c}	X	X ^k	X	X	X	X	X	X	X		X	X	X	X	X	X
Fundus Fluorescein Angiography ^{a,c}	X					X			X		X ^a	X ^a	X ^a	X	X	X
PK Sample ^a		X	X	X		X		X	X	X	X ^{m,q}	X ^{m,q}	X ^a	X	X	X
PD Biomarkers Sample ^a		X	X	X		X			X	X	X ^a	X ^a	X ^a	X	X	X
Exploratory Plasma Biomarkers Sample ^a		X				X			X					X	X	X
Clinical Genotyping Sample ^{a,g,h}		X														
Anti-Drug Antibody ^{a,f}		X	X	X		X		X	X		X ^a	X ^a	X ^a	X	X	X
Follow-Up Phone Call ^u									X ^s		X ^s	X ^s	X ^s			
Adverse Events	X	X	X	X	X	X	X	X	X	X	X	X	X	X	X	X
Previous and Concomitant Treatments	X	X	X	X	X	X	X	X	X	X	X	X	X	X	X	X

Assessment prior to study drug or ranibizumab administration on days when treatment is administered

a

b For females only

RO6867461—F. Hoffmann-La Roche Ltd
 Statistical Analysis Plan BP30099

- c Assessment in study eye only; except at screening for imaging assessments (FP, EDI SD-OCT, FFA), where either eye has a potential to meet all eligibility criteria
Finger count vision assessment asap after, and within maximum of 15 min from study drug or ranibizumab administration
- d Performed prior to pupil dilation
- e [REDACTED]
- f At day 1 but can be done at any other visit if the sample not collected at baseline
- g Mandatory, except in countries or at investigational sites where IFB/EC does not approve
- h [REDACTED]
- i [REDACTED]
- j Baseline assessments
- k IOP to be performed in both study and fellow eye. At visits with either study drug or ranibizumab administration the assessment post-treatment administration is in the study eye only. If IOP \geq 30 mmHg at 30 (5) minutes post-treatment administration in the study eye, then IOP is measured again at 60 (\pm 10) minutes. [REDACTED]
- l [REDACTED]
- m At the discretion of the investigator abnormal values might be followed-up at an unscheduled visit
- n
- o Optional at Day 1
The interval between two administrations of study drug needs to be at least 21 days
- p when this visit becomes the final visit
- q if pre-specified criteria are met
- r if patient receives ranibizumab at that visit
- s visit becomes final visit when patient receives 0.3 mg ranibizumab based on meeting pre-specified criteria
- t 7 days after
0.3 mg
ranibizumab
administration
(\pm 3 days)
- u

Appendix 3

Definition of ATE

ATE events are non-fatal stroke, non-fatal myocardial infarction, or vascular death (including deaths of unknown cause). They are defined as the following MedDRA terms/baskets:

Myocardial infarction

SMQ Broad | Myocardial infarction (SMQ)
PT | Coronary arterial stent insertion
PT | Coronary artery bypass
PT | Coronary endarterectomy
PT | Coronary revascularisation

Non-myocardial arterial thromboembolic events (ATEs)

SMQ Narrow | Haemorrhagic cerebrovascular conditions
SMQ Narrow | Ischaemic cerebrovascular conditions
PT | Amaurosis
PT | Amaurosis fugax
PT | Aortic bypass
PT | Aortic embolus
PT | Aortic surgery
PT | Aortic thrombosis
PT | Aortogram abnormal
PT | Arterectomy
PT | Arterectomy with graft replacement
PT | Arterial bypass operation
PT | Arterial graft
PT | Arterial occlusive disease
PT | Arterial stent insertion
PT | Arterial therapeutic procedure
PT | Arterial thrombosis
PT | Arteriogram abnormal
PT | Arteriogram carotid abnormal
PT | Atherectomy
PT | Blindness transient
PT | Carotid angioplasty
PT | Cerebral hypoperfusion
PT | Coeliac artery occlusion
PT | Embolia cutis medicamentosa
PT | Embolism
PT | Embolism arterial
PT | Endarterectomy
PT | Femoral artery embolism
PT | Femoral artery occlusion
PT | Hepatic artery embolism
PT | Hepatic artery occlusion
PT | Hepatic artery thrombosis
PT | Hypothenar hammer syndrome

PT | Iliac artery embolism
PT | Iliac artery occlusion
PT | Intra-aortic balloon placement
PT | Intraoperative cerebral artery occlusion
PT | Leriche syndrome
PT | Mesenteric arteriosclerosis
PT | Mesenteric artery embolism
PT | Mesenteric artery stenosis
PT | Mesenteric artery stent insertion
PT | Mesenteric artery thrombosis
PT | Microembolism
PT | Penile artery occlusion
PT | Percutaneous coronary intervention
PT | Peripheral arterial occlusive disease
PT | Peripheral arterial reocclusion
PT | Peripheral artery angioplasty
PT | Peripheral artery bypass
PT | Peripheral artery stent insertion
PT | Peripheral artery thrombosis
PT | Peripheral embolism
PT | Peripheral endarterectomy
PT | Popliteal artery entrapment syndrome
PT | Pulmonary artery therapeutic procedure
PT | Pulmonary artery thrombosis
PT | Pulmonary endarterectomy
PT | Renal artery angioplasty
PT | Renal artery occlusion
PT | Renal artery thrombosis
PT | Renal embolism
PT | Splenic embolism
PT | Stress cardiomyopathy
PT | Subclavian artery embolism
PT | Subclavian artery occlusion
PT | Subclavian artery thrombosis
PT | Superior mesenteric artery syndrome
PT | Thromboembolectomy
PT | Thrombotic microangiopathy
PT | Thrombotic thrombocytopenic purpura
PT | Truncus coeliacus thrombosis
PT | Visual acuity reduced transiently

Venous thromboembolism

PT | Axillary vein thrombosis
PT | Budd-Chiari syndrome
PT | Catheterisation venous
PT | Cavernous sinus thrombosis
PT | Central venous catheterisation
PT | Cerebral venous thrombosis
PT | Compression stockings application
PT | Deep vein thrombosis

PT | Deep vein thrombosis postoperative
PT | Embolism
PT | Embolism venous
PT | Hepatic vein occlusion
PT | Hepatic vein thrombosis
PT | Homans' sign positive
PT | Iliac vein occlusion
PT | Inferior vena cava syndrome
PT | Inferior vena caval occlusion
PT | Intracranial venous sinus thrombosis
PT | Intravenous catheter management
PT | Jugular vein thrombosis
PT | May-Thurner syndrome
PT | Mesenteric vein thrombosis
PT | Obstetrical pulmonary embolism
PT | Obstructive shock
PT | Ovarian vein thrombosis
PT | Paget-Schroetter syndrome
PT | Pelvic venous thrombosis
PT | Penile vein thrombosis
PT | Phlebectomy
PT | Phleboplasty
PT | Portal vein cavernous transformation
PT | Portal vein occlusion
PT | Portal vein thrombosis
PT | Post procedural pulmonary embolism
PT | Post thrombotic syndrome
PT | Postoperative thrombosis
PT | Postpartum venous thrombosis
PT | Pulmonary embolism
PT | Pulmonary infarction
PT | Pulmonary microemboli
PT | Pulmonary thrombosis
PT | Pulmonary vein occlusion
PT | Pulmonary veno-occlusive disease
PT | Pulmonary venous thrombosis
PT | Renal vein embolism
PT | Renal vein occlusion
PT | Renal vein thrombosis
PT | SI QIII TIII pattern
PT | Splenic vein occlusion
PT | Splenic vein thrombosis
PT | Subclavian vein thrombosis
PT | Superior sagittal sinus thrombosis
PT | Superior vena cava syndrome
PT | Thrombophlebitis
PT | Thrombophlebitis migrans
PT | Thrombophlebitis neonatal
PT | Thrombophlebitis superficial
PT | Thrombosed varicose vein
PT | Thrombosis corpora cavernosa

PT | Transverse sinus thrombosis
PT | Vascular graft
PT | Vena cava embolism
PT | Vena cava filter insertion
PT | Vena cava thrombosis
PT | Venogram abnormal
PT | Venoocclusive disease
PT | Venoocclusive liver disease
PT | Venous occlusion
PT | Venous operation
PT | Venous recanalisation
PT | Venous stent insertion
PT | Venous thrombosis
PT | Venous thrombosis in pregnancy
PT | Venous thrombosis limb
PT | Venous thrombosis neonatal

Appendix 4

Imaging Variables not listed as primary or secondary endpoints

Imaging Modality	Outcome Variable	Detailed Definition	Variable names used by central reading center
SD-OCT	Total macular volume	Cube Volume (mm3) ILM-RPE - Reader 1-3	OCTTotalMaculaVolume1-3
	Epiretinal Membrane		OCTEpiretinalMembrane
FFA	Macular perfusion and leakage		FAMaculalschemiaArea1-3 FAMaculalschemiaAreaB1-3 FAMaculalschemiaNone
	Peripheral perfusion and leakage		FANonMaculaCapillaryNonperfusionArea FANonMaculaCapillaryNonperfusionAreaB1-3 FANonMaculaCapillaryNonperfusionNone
	Prior Macular Laser	Prior Macular Laser by FFA- Red-free present	RFPriorMacularLaser
	Prior Macular Laser	Prior Macular Laser by FFA present	FAMaculaPriorMacularLaserNone
	Prior PRP	Prior panretinal photocoagulation by FFA present	FANonMaculaPriorPRP
	Focal Edema	Macula focal leakage	FAMaculaMEFocalLeakage
	Diffuse Edema	Macula diffuse leakage	FAMaculaMEDiffuseLeakage
	Cystoid Edema	Cystoid edema	FAMaculaCystoidEdema
Fundus Color Photography	Cup/Disk Ratio		ColorCuptoDiskRatio1-3
	Diabetic retinopathy severity scale		DRSS
	Prior Macular Laser	Prior Macular Laser by FP present	ColorPriorMacularLaser
	Prior PRP	Prior panretinal photocoagulation by FP present	ColorNonMaculaPriorPRP

Baseline Ocular Characteristics

1. Cataracts - Use Medical History as source for the Baseline Ocular table.
2. Pan Retinal Photocoagulation laser - Targeted Surgeries and Procedures eCRF page
3. Peripheral Ischemia/Perfusion - Use FANonMaculaCapillaryNonperfusionNone, alongside FANonMaculaCapillaryNonperfusionArea for area size

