3.6 SAFETY ANALYSES

All safety analyses will be based on the safety analysis population. The LoPO contains the full list of reports for safety analyses.

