3.6.1 Adverse Events

The original terms recorded on the eCRF by the Investigators for adverse events will be standardized by the Sponsor. Adverse events will be summarized by mapped term and appropriate thesaurus level, including separate exploratory analyses of ATE events (Appendix 3).

Separate summaries will be prepared for systemic and ocular adverse events, with events in the study eye and non-study eye summarized separately. SAEs will be summarized similarly. Adverse events leading to discontinuation from the study will be listed and tabulated.

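### SAP Appendix 3 states a three-part ATE composite but implements it with term lists that add venous and other events and give unknown-cause deaths no stated route in

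*SAP*

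**What the plan says.** SAP 3.6.1 plans AE summaries by mapped term, "including separate exploratory analyses of ATE events (Appendix 3". It gives no derivation rule of its own.

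Appendix 3 opens with a definition in words: "ATE events are non-fatal stroke, non-fatal myocardial infarction, or vascular death (including deaths of unknown cause". The next sentence ties those events to term lists: "They are defined as the following MedDRA terms/baskets". Three lists follow, and none is exempted:

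- a myocardial infarction basket;
- a basket headed "Non-myocardial arterial thromboembolic events (ATEs", so the same abbreviation also labels this list alone;
- a basket headed "Venous thromboembolism".

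On deaths, Protocol 5.3.5.7 treats death as an outcome and has the causing event recorded. If the cause is unknown, the entry is *unexplained death*. The term *sudden death* is kept for abrupt deaths presumed to be cardiac.

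For the outputs themselves, SAP 3.6 refers to a separate list: "The LoPO contains the full list of reports for safety analyses". That list is not among the documents.

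**The concern.** The definition and its implementation select different events. A programmer who follows the term lists would count a non-fatal deep vein thrombosis, or an application of compression stockings, as an ATE. The same programmer would have no instruction that brings in a death of unknown cause, although the definition includes such deaths.

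Protocol 1.3 commits to monitoring systemic effects associated with intravitreal VEGF inhibitors, and the ATE output is the place where the SAP looks at arterial events as a group. A reader of that table would take the count to be the stated composite, and it would not be.

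**Working it through.** The plan states no count of terms, so there is no figure of its own to reproduce. The check counts the printed lists and sets them against the definition.

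**Step 1. Count the lists in Appendix 3.**

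| Basket | SMQs | PT lines |
|---|---|---|
| Myocardial infarction | 1 (broad) | 4 |
| Non-myocardial arterial | 2 (narrow) | 72 |
| Venous thromboembolism | 0 | 75 |
| Total | 3 | 151 |

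PT lines: 4 + 72 + 75 = 151. *Embolism* stands in both the arterial and the venous list, so there are 151 − 1 = 150 distinct PTs. Without the venous basket, 3 SMQs and 4 + 72 = 76 PTs remain.

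**Step 2. Venous basket against the definition.** A non-fatal venous event is not a stroke, a myocardial infarction or a death. A fatal one, such as a fatal pulmonary embolism, might be a vascular death, but the SAP does not define that term. So non-fatal venous events are clearly outside the composite, and fatal ones are undecided.

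**Step 3. The other two baskets against the definition.** Sorted by name:

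- The 4 PTs in the myocardial infarction basket are all procedures.
- The 72 arterial PTs include 22 procedures, 3 abnormal-imaging terms and 4 vision-loss terms, which leaves 72 − 22 − 3 − 4 = 43. Many of these 43 are arterial diagnoses other than stroke, for example *Femoral artery occlusion*.
- The arterial basket, although headed as non-myocardial, also holds *Percutaneous coronary intervention*.

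By their titles, the three SMQs carry the infarction and stroke terms. Their contents are not in the documents.

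**Step 4. Deaths.** None of the 151 PT lines names a death. In the SAP text available, fatality and death are mentioned only in the definition sentence. So no printed PT and no outcome rule picks up *unexplained death* or *sudden death* as recorded under Protocol 5.3.5.7. The definition does include unknown-cause deaths; what is missing is the rule that implements this.

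**Step 5. Fatal versus non-fatal.** A fatal infarction or stroke is a vascular death, so it belongs to the composite whether or not it is labelled fatal. Protocol 5.3.5.7 has the causing event recorded, so such a case would be entered under that event. The missing fatal/non-fatal rule therefore leaves the breakdown by component undefined but does not change the total for infarction and stroke.

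**Step 6. Size.** No event rates are given, so no change in counts can be computed. As a scale only, planned arm sizes are 50 + 30 = 80 in Arms A and C and 50 in Arm B. One misclassified patient moves an arm's ATE percentage by 1/80 = 1.25 points or 1/50 = 2.0 points.

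**The case against.** The best defence is that the three baskets were meant to be tabulated separately. They have separate headings, SAP 3.6.1 speaks of analyses in the plural, and the list of planned outputs may settle it. That reading is plausible, but no text in the SAP states it. Nor would it deliver the stated composite: *Embolism* would appear in two tables, the arterial basket goes well beyond stroke, and unknown-cause deaths would still have no route in.

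It is also fair to say that a broad search is a legitimate exploratory safety tool. It is, under its own title. The fault lies in giving it the composite's name.

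Several stronger readings are tempting, and the documents do not support them:

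- *Half of the ATE events would be venous.* The venous list is 75/151 = 49.7% of the PT lines, but a share of lines says nothing about how often events occur, and the SMQs are not in that count.
- *The whole venous list lies outside the definition.* Vascular death is not limited to arterial causes, so fatal venous events could qualify.
- *The composite cannot be formed without a fatal/non-fatal split.* Only the component breakdown needs it (Step 5).
- *Deaths of unknown cause are lost.* They would still appear by mapped term in the AE and SAE summaries.
- *Vision-loss terms such as "PT | Visual acuity reduced transiently" show that an eye rule is missing.* SAP 3.6.1 already has a general one: "Separate summaries will be prepared for systemic and ocular adverse events, with events in the study eye and non-study eye summarized separately". Not repeating it for a single output is not a defect.

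**Conclusion.** Wrong as written, and minor. The definition in words and the term lists in Appendix 3 do not select the same events, and the text says that the lists define the events. Taken literally, the output would include non-fatal venous events and many arterial, procedure and imaging terms that the definition leaves out. It would also contain no stated route for unknown-cause deaths that the definition includes.

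The effect is confined to one exploratory safety output. No efficacy test or decision rule depends on it, and the events remain visible elsewhere in the safety tables.

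Confidence is high for the mismatch in the text. It is lower for any actual miscount, which depends on the SMQ contents, on the list of planned outputs and on which events occur.

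**What to change.** Amend Appendix 3 before unmasking:

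1. Remove the venous basket from the ATE definition and tabulate it under its own VTE title. Assign *Embolism* to one list only.
2. Define vascular death, and say whether fatal venous events such as fatal pulmonary embolism count. Use the recorded AE outcome to bring in vascular deaths and deaths recorded as *unexplained death* or *sudden death*. The same outcome field gives the fatal/non-fatal component split.
3. Report the stated composite under the ATE title. Keep the broader arterial and procedure basket as a sensitive search with a different title.

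The cost is a short appendix edit and a little extra programming. The sponsor already tabulated AEs with a fatal outcome for the Phase I study (Protocol Table 1). The narrower composite will hold fewer events, which is the reason to keep the broader search beside it.
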